10.4. Appendix 4: Pregnancy Information

Definitions

Woman of Childbearing Potential

A woman is considered fertile following menarche and until becoming postmenopausal unless permanently sterile (see below).

Women in the Following Categories are Not Considered Women of Childbearing Potential

- 1. Premenopausal female with 1 of the following:
 - Documented hysterectomy
 - Documented bilateral salpingectomy
 - Documented bilateral oophorectomy
 - Note: Documentation can come from the site personnel's review of the subject's medical records, medical examination, or medical history interview.
- 2. Postmenopausal female
 - A postmenopausal state is defined as no menses for 12 months without an alternative medical cause and a documented serum follicle-stimulating hormone level ≥ 40 mIU/mL during screening. A high FSH level in the postmenopausal range must be used to confirm a postmenopausal state in women not using hormonal contraception or hormonal replacement therapy (HRT). However, in the absence of 12 months of amenorrhea, a single FSH measurement is insufficient.
 - Female subjects on HRT and whose menopausal status is in doubt will be required to use one of the non-estrogen hormonal highly effective contraception methods if they wish to continue their HRT during the study. Otherwise, they must discontinue HRT to allow confirmation of postmenopausal status before study enrollment.

Pregnancy Testing

• Women of childbearing potential should only be included after a negative serum pregnancy test. Additional pregnancy testing should be performed per the time points specified in the Schedule of Activities (Table 1 and Table 2).

Collection of Pregnancy Information

- Pregnancy data will be collected during this study for all subjects and a female spouse/partner of male subjects. Exposure during pregnancy (also referred to as exposure in utero) can be the result of either maternal exposure or transmission of drug product via semen following paternal exposure.
- If a female subject participating in this study or a male subject's female sexual partner of childbearing potential becomes or is found to be pregnant while being treated or exposed to study drug, the Investigator must submit the "Pregnancy Reporting and Outcome/Breast Feeding Form" to the Sponsor or designee via the same method as

SAE reporting. (Section 10.3 [Appendix 3]). When the outcome of the pregnancy becomes known, the form should be updated and submitted to the Sponsor's GPV. If additional follow-up is required, the Investigator will be requested to provide the information.

- Exposure of an infant to a Sponsor product during breastfeeding must also be reported (via the "Pregnancy Reporting and Outcome Form/Breastfeeding" form) and any AEs experienced by the infant must be reported to the Sponsor's GPV or designee via facsimile or email (Section 10.3 [Appendix 3]).
- A pregnancy in itself is not regarded as an AE unless there is a suspicion that the study drug may have interfered with the effectiveness of a contraceptive medication. However, complications of pregnancy and abnormal outcomes of pregnancy are AEs and may meet the criteria for an SAE (eg, ectopic pregnancy, spontaneous abortion, intrauterine fetal demise, neonatal death, or congenital anomaly). Elective abortions without complications should not be reported as AEs (Section 8.3.5).
- Any female subject who becomes pregnant while participating in the study may not be withdrawn from the study.

10.5. Appendix 5: Abbreviations

[figure not shown]
The following abbreviations and terms are used in this study protocol.

 Table 10:
 Abbreviations and Specialist Terms

[figure not shown]
Abbreviation or		
Term	Explanation	
ADA	antidrug antibody	
AE	adverse event	
aHUS	atypical hemolytic uremic syndrome	
ALT	alanine aminotransferase	
AST	aspartate aminotransferase	
AUC∞	area under the serum concentration versus time curve from zero to infinity	
BMI	body mass index	
CAP	complement alternative pathway	
CH50	50% hemolytic complement activity (screening test for deficiency of classical	
	complement pathway in which hemolysis of liposomes sensitized by specific	
	antibodies is measured; one CH50 unit is the volume or dilution of serum that lyses	
	50% of liposomes)	
CL	total body clearance of drug from the serum	
C _{max}	maximum observed serum concentration	
cRBC	chicken red blood cell	
CRU	clinical research unit	
CTCAE	Common Terminology Criteria for Adverse Events	
CV	coefficient of variation	
ECG	electrocardiogram	
eCRF	electronic case report form	
EOI	End-of-infusion	
F	absolute bioavailability	
Frel	relative bioavailability	
FSH	Follicle-stimulating hormone	
GCP	Good Clinical Practice	
GPV	Global Pharmacovigilance	
HA	hyaluronic acid	
HBcAb	hepatitis B core antibody	
HBsAb	hepatitis B surface antibody	
HBsAg	hepatitis B surface antigen	
HIV	Human immunodeficiency virus	
HRT	hormone replacement therapy	
IB	Investigator's Brochure	
ICF	informed consent form	
ICH	International Council for Harmonisation of Technical Requirements for	
150	Pharmaceuticals for Human Use	
IEC	independent ethics committee	
IRB	institutional review board	
IV	intravenous(ly)	
mAb	monoclonal antibody	
MCV4	tetravalent meningococcal conjugate vaccine	
OP	outpatient	
PD	pharmacodynamic(s)	
PK	pharmacokinetic(s)	
PNH	paroxysmal nocturnal hemoglobinuria	
QTcF	QT interval corrected using the Fridericia's formula	

Abbreviation or	
Term	Explanation
rHuPH20	recombinant human hyaluronidase PH20
SAE	serious adverse event
SAP	statistical analysis plan
SC	subcutaneous(ly)
SOC	System Organ Class
SOI	Start-of-infusion
SRC	Safety Review Committee
ТВ	tuberculosis
TEAE	treatment-emergent adverse events
ULN	upper limit of normal
Vd	volume of distribution

1. INTRODUCTION

The purpose of this Statistical Analysis Plan (SAP) is to define the variables and analysis methodology to address the study objectives.

The protocol dated 20 Jul 2018, Amendment 1, was used in the preparation of this SAP.

Pharmacokinetic (PK) parameters calculations and statistical analyses will be the responsibility of Richmond Pharmacology Ltd (RPL). Tables, figures, and listings (TFLs) will be produced using Statistical Analysis Software (SAS), Version 9.3 or higher.

2. STUDY OBJECTIVES AND ENDPOINTS

2.1 Study objectives

The objectives of this study are:

Primary

- To estimate the absolute bioavailability of subcutaneous (SC) ravulizumab coadministered with recombinant human hyaluronidase PH20 (rHuPH20)
- To assess the safety and tolerability of ravulizumab SC/rHuPH20.

Secondary

- To estimate the relative bioavailability of ravulizumab SC/rHuPH20 compared with ravulizumab SC.
- To explore the pharmacodynamic (PD) effects of ravulizumab SC coadministered with rHuPH20

2.2 Endpoints

Primary

- Serum concentration of ravulizumab will be used to determine the geometric mean ratio of the area under the concentration time curve (AUC) values
- Safety assessed by incidence of treatment-emergent adverse events (TEAEs) and serious adverse events, physical examination, vital sign measurements, clinical laboratory and electrocardiogram (ECG) results, and measurement of antidrug antibodies (ADA).

Secondary

- Serum concentration of ravulizumab will be used to determine the geometric mean ratio of the AUC values
- Change in serum levels of total and free complement component 5 (C5) concentrations over time
- Change in ex vivo chicken red blood cell (cRBC) hemolysis activity over time

3. TRIAL DESIGN

This is a Phase 1 study designed to evaluate the safety, tolerability, PK, PD, immunogenicity, and absolute and relative bioavailability of single ascending doses of ravulizumab SC coadministered with rHuPH20 compared to a single dose of ravulizumab intravenous (IV) 400 mg or a single dose of ravulizumab SC 400 mg in 48 healthy adult subjects. Five treatment cohorts are planned.

A Safety Review Committee (SRC) will evaluate the study data for subject safety and make recommendations on dose escalation, dose modification, or termination of the study. When cohorts are being enrolled in parallel, subject assignment to a cohort will be done through randomization. The study will be conducted at a single site in the United Kingdom (UK).

3.1 Overall Design

Eighteen subjects will be randomly assigned in a 1:2 ratio between the first two cohorts to receive either a single dose of ravulizumab SC 400 mg (Cohort 1, n = 6) or a single dose of ravulizumab SC 500 mg/rHuPH20 10,000 units (Cohort 2, n = 12). The SRC will review Cohort 2 ravulizumab SC/rHuPH20 safety data and make their recommendation for escalating the dose of the ravulizumab SC/rHuPH20 cohort.

If the SRC recommendation following the review of data from Cohort 2 is to initiate the next cohort and proceed with the planned dose escalation, 18 subjects will be randomly assigned in a 2:1 ratio between Cohort 3 (n = 12) and Cohort 5 (n = 6) to receive either a single dose of ravulizumab SC 1000 mg/rHuPH20 20,000 units or a single dose of ravulizumab IV 400 mg, respectively. The SRC will subsequently review Cohort 3 ravulizumab SC/rHuPH20 safety data and make their recommendation to proceed with planned dose escalation in Cohort 4 or a reduced dose in Cohort 4.

Whether the SRC recommendation is to initiate Cohort 4 with the planned dose escalation or at a reduced dose, 12 subjects will be enrolled in Cohort 4 to receive a single dose of ravulizumab SC/rHuPH20 (dose to be determined based on SRC recommendation).

If the recommendation following the review of ravulizumab SC/rHuPH20 safety data from Cohort 2 is to proceed with Cohort 3 at a reduced dose, 18 subjects will be randomly assigned in a 2:1 ratio between Cohort 3 (n = 12) and Cohort 5 (n = 6) to receive either a single dose of ravulizumab SC/rHuPH20 (dose to be determined based on SRC recommendation) or a single dose of ravulizumab IV 400 mg, respectively. In this scenario, Cohort 4, if conducted, will be enrolled at a reduced dose, following completion of Cohort 3 based on SRC review of ravulizumab SC/rHuPH20 safety data from Cohort 3 and a favorable recommendation to enroll subjects in Cohort 4.

If the SRC determines that no further ravulizumab SC/ rHuPH20 combination dosing cohorts should be enrolled following Cohort 2, then Cohort 5 may still be enrolled as a stand-alone cohort at the discretion of the Sponsor.

[figure not shown]
Cohort	N	Study Drug	Route (SC/IV)	Planned Dose
1	6	ravulizumab	SC	400 mg
2	12	ravulizumab/rHuPH20	SC	500 mg / 10,000 units
3	12	ravulizumab/rHuPH20	SC	1000 mg / 20,000 units
4	12	ravulizumab/rHuPH20	SC	2000 mg / 40,000 units
5	6	ravulizumab	IV	400 mg

Table 1: ALXN1210-HV-105 Study Design

3.2 Duration of Study

The planned study duration is approximately 39 weeks; up to 70 days for screening and approximately 200 days for dosing and follow-up. For the first 5 days during the Dosing and Follow-up Period, subjects will be admitted to an inpatient facility. Dosing will be staggered within and between cohorts, but the end of study for each individual subject is anticipated to be Day 200 or the time point at which complement activity has normalized, if later than Day 200.

Note: Subjects will be randomly assigned to Cohort 1 or Cohort 2, randomly assigned to Cohort 3 or Cohort 5, and sequentially assigned to Cohort 4.

Figure 1: Study ALXN1210-HV-105 Schematic

3.3 Sample Size

The sample size is based on PK rather than statistical considerations. A total sample size of 48 subjects (6 subjects each in the control cohorts [Cohort 1 and 5] and 12 subjects each in the combination cohorts [Cohorts 2, 3, and 4]) will serve to estimate bioavailability.

3.4 Randomization and Blinding

This is an open-label study. Eligible subjects who meet all inclusion and no exclusion criteria will be assigned unique numbers for enrollment and randomization. Randomization will only be used when cohorts are being enrolled in parallel.

 In order to minimize selection bias in treatment assignment, subjects will be randomly or sequentially assigned subject numbers, depending upon cohort, up to 7 days prior to dosing on Day 1, in the same order as they have become eligible.

^a Dosing will be staggered, but the end of study for each subject is Day 200 or the time point at which complement activity has normalized, if later than Day 200.

^b For Cohorts 1 through 4, a sentinel dosing approach will be used (ie, 2 subjects in a cohort with 12 subjects and 1 subject in a cohort with 6 subjects will be dosed prior to dosing the remaining subjects within the cohort). Abbreviations: D = day; IV = intravenous; N = number [of subjects]; SC = subcutaneous.

- Sentinel dosing will be employed in Cohorts 1 through 4 (ie, 2 subjects in a cohort with 12 subjects and 1 subject in a cohort with 6 subjects will be dosed prior to dosing the remaining subjects within the cohort). Remaining subjects within the cohort will be dosed at least 24 hours following dosing of the sentinel subjects.
- At the Sponsor's discretion, and after consultation with the SRC, up to 16 additional subjects may be enrolled as replacement subjects if any subject discontinues prior to Day 50 for reasons other than drug-related adverse events (AE).
- Study numbers will not be reallocated once assigned

4. STATISTICAL ANALYSES

In general, descriptive statistics for continuous variables will include number of non-missing values (n), arithmetic mean, standard deviation (SD), median, minimum, and maximum.

Descriptive statistics for PK parameters will include number of observations (n), arithmetic mean, standard deviation (SD), arithmetic coefficient of variation (%CV), geometric mean, geometric %CV, median, minimum and maximum.

Categorical variables will be summarized using frequency counts and percentages.

For all tables, except PK parameter tables, descriptive statistics for minimum and maximum will be presented with the same decimal digits as the original data, and with 1 more decimal place than the original data for mean and median; SD will be reported with 2 more decimal places than the original data.

PK parameters will be presented as follows in the listing: Cmax and Tmax will be presented as given in the raw data; AUC0-t, AUC0- ∞ , λz , t1/2, CL or CL/F, and Vd or V_d/F will be presented with 3 decimal places, that is special characters will not be presented in the tables, listings or figures. Descriptive statistics for PK parameters will be presented with decimal places as appropriate for the particular parameter and treatment group.

The analyses will be presented by treatment group, i.e. cohorts. All collected data will be presented in by-subject listings. Listings will be ordered by treatment group and subject number and will include all randomized subjects.

Baseline will be defined as the last non-missing value among assessments recorded prior to first administration of study drug. Changes from baseline values will be calculated as the post-baseline assessment value minus the baseline value. Only observed values from scheduled time points will be used to create summary tables.

Early Termination (ET) visits will be recoded to ET visits where necessary and reported as ET.

Deviations from the planned analyses will be described in the final clinical study report (CSR).

Page layout of the TFLs will be in landscape mode and will be provided in Microsoft Word. Final TFLs will additionally be created as bookmarked PDF. Further details of page layout will be provided in the TFL shell document. Individual RTF files for tables may be provided to assist medical writing. RTF files will not be compiled into a single document.

4.1 Interim Analysis

An interim assessment of PK data through Day 50 may be performed.

4.2 Analysis Populations

Inclusion and exclusion from each analysis set will be decided at the Blind Data Review Meeting (BDRM) prior to database lock. Further exclusions may be made from PK/PD/Immunogenicity sets based on the concentrations.

Safety Population

The safety population will consist of all subjects who receive at least 1 dose of the study drug.

PK Population

The PK population will consist of all subjects who have sufficient serum concentration data to enable the calculation of PK parameters of at least Area Under the Curve (AUC). Subjects who did not receive the full dose of study drug will be excluded from the PK population.

PD Population

The PD population will consist of all subjects who have sufficient free C5 concentration data which will enable the evaluation of the PD effects. Subjects who are replaced will not be included in the PD population.

Immunogenicity Population

The immunogenicity population will consist of all subjects who have a predose and post-dose ADA sample collected.

4.3 Subject Disposition

All subjects will be included in the summary of subject disposition. This will present the overall number of subjects screened and by treatment group and overall the frequency and percentage of subjects randomized and treated, and who completed or discontinued from the study, along with reason for discontinuation.

Furthermore, the number and percentage of subjects in each study population will be tabulated. Discontinued subjects will be listed. Subject assignment to study populations will be listed. Screen Failures will not be listed or included in summary tables.

4.4 Demographic Characteristics

Individual subject demographics (including age, sex, race and ethnicity) and body measurement data (height, body weight and body mass index) at screening will be listed and summarized by each treatment group and overall for the safety population. If the remaining populations are different from the safety population by more than 5%, separate demographic tables will be produced.

Height will be measured in centimeters and weight in kilograms. Body mass index will be given in kg/m^2 .

4.5 Baseline and Other Safety Characteristics

Data collected from vaccine and antibiotic prophylaxis, vaccine titer, tuberculosis testing, virus serology, serum pregnancy test, alcohol breath test and urine drug screen will be listed by subject.

4.6 Inclusion and Exclusion Criteria

The inclusion and exclusion criteria will be listed together with the overall eligibility for each subject.

4.7 Protocol Deviations

The final review of protocol deviations will be performed at the BDRM prior to database lock. The protocol deviations will be listed.

4.8 Medical History

Medical history data will be coded using the Medical Dictionary for Regulatory Activities (MedDRA) dictionary Version 21.0 (or higher) and listed individually. Surgical histories will be listed separately.

4.9 Study Drug Administration

Study drug administration data will be listed individually.

4.10 Prior and Concomitant Medications

All prior and concomitant medications will be coded using the World Health Organization Drug Dictionary version June 1, 2018 or higher and will be listed individually. The frequency and percentage of prior and concomitant medications will be summarized by Anatomical Therapeutic Chemical and Preferred Name. Separate tables will be given for prior and concomitant medications. Prior medications are defined as those for which the end date and time is prior to the date, and time of first study drug administration. Concomitant medications are defined as those with start date and time on or after the date and time of first study drug administration and those with start date and time prior to the first study drug administration but with end date an time on or after the date and time of first

study drug administration. Non-pharmacologic therapies and procedures and prophylactic antibiotic treatment will be listed.

Prior and concomitant medications with missing start (end) date or time will be classified as concomitant medication.

4.11 Infusion/Injection Site (Pain) Evaluation

Data from the injection/infusion site evaluations and from pain at infusion/injection site will be listed individually. Injection/infusion site evaluations will be summarized by treatment group.

4.12 Safety Analysis

Safety analyses will be performed on the safety population, and will be reported at each time point by treatment group, reporting criteria will be outlined for each safety parameter Safety parameters will also be summarized overall and for the rHuPH20 treatment groups combined.

Safety analyses will include an analysis of all AEs, ECGs, clinical laboratory data, vital sign measurements and physical examination results and will be presented using descriptive statistics. No inferential statistical analyses are planned on the safety parameters of this study.

4.12.1 Adverse Events

A Treatment Emergent Adverse Event (TEAE) is any adverse event that commences after the start of administration of study drug.

The incidence of TEAEs (after dosing) will be summarized using the safety population. The MedDRA dictionary Version 21.0 (or higher) will be used to classify all AEs reported during the study by System Organ Class (SOC) and Preferred Term. A summary of TEAEs including the incidence of subjects who experienced TEAEs (number and percentage of subjects) and incidence of TEAEs (number of events) will be presented for each treatment group and overall, by severity and by relationship to study drug.

TEAEs and serious TEAEs will be summarized by SOC and Preferred Term for each treatment group and overall, and by relationship to study drug.

Subjects having multiple AEs within a category (e.g., overall, SOC and Preferred Term) will be counted once in that category. For severity tables, a subject's most severe event within a category will be counted. For relationship tables, a subject's event with greatest relationship to study drug within a category will be counted. In each table, SOC and Preferred Term will be presented in descending order of overall incidence rate (alphabetical order will be used in case of equal rates).

All adverse events will be listed. Serious TEAEs will be listed, if required.

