8.2.9. Vaccine and Antibiotic Prophylaxis

To mitigate the risk of *N meningitidis* infection associated with terminal complement inhibition, subjects in this study will be administered the following:

- 1. A MCV4 vaccination at least 56 days prior to dosing of ravulizumab on Day 1 (if not vaccinated with MCV4 within the last 3 years, or if subjects have been previously vaccinated but there is not adequate documentation to verify prior vaccination).
- 2. Two injections of the serogroup B meningococcal vaccine. The first injection must be administered at least 56 days prior to dosing on Day 1, with a booster administered at least 28 days prior to dosing on Day 1, with at least 28 days between the first and second injections.
- 3. Prophylactic antibiotic treatment, oral penicillin V 500 mg twice daily (equivalent to 1×10^6 units) until complement activity has normalized (as determined by CH50 assay).

The first dose of antibiotic will be administered orally on Day -1 in the evening, prior to the Day 1 (dose administration) of study drug. For the outpatient portion of the study, subjects will be instructed to take the antibiotic approximately at the same times (twice daily) on each scheduled day. A suitable system (such as text messaging) will be used for daily monitoring of subjects' compliance with the antibiotic prophylaxis regimen.

The following observations support the administration of antibiotic prophylaxis in this single-dose study:

- 1. Penicillin is the drug of choice in eradication of *N meningitidis* in carriers.
- 2. Complement-deficient patients who received monthly injections with benzathine penicillin G as prophylaxis for recurrent meningococcal disease during a 2- to 4-year period experienced significantly fewer episodes of *Neisseria* infection than deficient individuals not receiving prophylaxis (Figueroa, 1991).

- 3. High levels of resistance to penicillin caused by plasmid-encoded β -lactamases are rarely encountered in meningococcal strains (Yazdankhah, 2004).
- 4. Antibiotic prophylaxis with orally administered penicillin V 500 mg twice daily has been provided in the treatment of PNH and aHUS patients with eculizumab by some physicians and is generally well-tolerated (Kelly, 2011; Leeds Teaching Hospitals NHS Trust, 2013).

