8.3. Adverse Events and Serious Adverse Events

The definitions of an AE or SAE and specific reporting requirements are located in Section 10.3 (Appendix 3). Adverse events will be reported to the Investigator or qualified designee by the subject (or, when appropriate, by a caregiver, surrogate, or the subject's legally authorized representative).

The Investigator and any qualified designees are responsible for detecting, documenting, and recording events that meet the definition of an AE or SAE and remain responsible for following up AEs that are serious, considered related to the study drug or study procedures, or that caused the subject to discontinue the study drug (see Section 7).

8.3.1. Time Period and Frequency for Collecting Adverse Event and Serious Adverse Event Information

All AEs and SAEs will be collected from the signing of the ICF until the last follow-up visit.

Medical occurrences that begin before the start of study drug and after obtaining informed consent will be recorded on the eCRF, and will be considered as medical history.

All SAEs will be recorded and reported to the Sponsor or designee within 24 hours, as indicated in Section 10.3 (Appendix 3). The Investigator will submit updated SAE data to the Sponsor within 24 hours of the data being available.

Investigators are not obligated to actively seek AEs or SAEs after the conclusion of study participation (ie, after Day 200).

The method of recording, evaluating, and assessing causality of AEs and SAEs and the procedures for completing and transmitting SAE reports to Sponsor are provided in Section 10.3 (Appendix 3).

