Complement	The results of each test must be entered into the eCRF.Complement activationCH50Total and free C5productorCH50Total and free C5		Total and free C5
Activity	products		

Table 9: Protocol-Required Safety Laboratory Assessments

10.3. Appendix 3: Adverse Events: Definitions and Procedures for Recording, Evaluating, Follow-up, and Reporting

Adverse Event Definition

- An AE is any untoward medical occurrence in a patient or clinical study subject, temporally associated with the use of study drug, whether or not considered related to the study drug.
- NOTE: An AE can therefore be any unfavorable and unintended sign (including an abnormal laboratory finding), symptom, or disease (new or exacerbated) temporally associated with the use of study drug.

Events Meeting the Adverse Event Definition

- Any abnormal laboratory test results (hematology, clinical chemistry, or urinalysis) or other safety assessments (eg, ECG, radiological scans, vital signs measurements), including those that worsen from baseline, considered clinically significant in the medical and scientific judgment of the Investigator (ie, not related to progression of underlying disease).
- New conditions detected or diagnosed after study drug administration even though it may have been present before the start of the study.
- Signs, symptoms, or the clinical sequelae of a suspected drug-drug interaction.

Events NOT Meeting the Adverse Event Definition

- Medical or surgical procedure (eg, endoscopy, appendectomy): the condition that leads to the procedure is the AE.
- Situations in which an untoward medical occurrence did not occur (social and/or convenience admission to a hospital).
- Anticipated day-to-day fluctuations of pre-existing disease(s) or condition(s) present or detected at the start of the study that do not worsen.

Serious Adverse Event Definition

If an event is not an AE per definition above, then it cannot be a SAE even if serious conditions are met (eg, hospitalization for signs/symptoms of the disease under study, death due to progression of disease).

A serious adverse event is defined as any untoward medical occurrence that, at any dose: 1. Results in death

2. Is life-threatening

The term 'life-threatening' in the definition of 'serious' refers to an event in which the subject was at risk of death at the time of the event. It does not refer to an event, which hypothetically might have caused death, if it were more severe.

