- The Investigator will then record all relevant AE or SAE information in the eCRF.
- It is not acceptable for the Investigator to send photocopies of the subject's medical records to the Sponsor or designee in lieu of completion of the AE/SAE eCRF page.
- There may be instances when copies of medical records for certain cases are requested by the Sponsor or designee. In this case, all subject identifiers, with the exception of the subject number, will be redacted on the copies of the medical records before submission.
- The Investigator will attempt to establish a diagnosis of the event based on signs, symptoms, and/or other clinical information. Whenever possible, the diagnosis (not the individual signs/symptoms) will be documented as the AE/SAE.

Assessment of Intensity

The Investigator will make an assessment of intensity for each AE and SAE reported during the study and assign it to 1 of the following categories from National Cancer Institute CTCAE v4.03, published 14 Jun 2010:

- Grade 1: Mild (awareness of sign or symptom, but easily tolerated)
- Grade 2: Moderate (discomfort sufficient to cause interference with normal activities)
- Grade 3: Severe (incapacitating, with inability to perform normal activities)
- Grade 4: Life-threatening
- Grade 5: Fatal

Changes in the severity of an AE should be documented to allow an assessment of the AE duration at each level of intensity to be evaluated. Adverse events characterized as intermittent require documentation of onset and duration of each episode, if the severity of the intermittent event changes.

An event is defined as 'serious' when it meets at least 1 of the predefined outcomes as described in the definition of an SAE, NOT when it is rated as severe.

Assessment of Causality		
• The Investigator is obligated to assess the relationship between study drug and each occurrence of each AE/SAE. An Investigator causality assessment must be provided for all AEs (both nonserious and serious). This assessment must be recorded in the data capture system and on any additional forms, as appropriate. The definitions for the causality assessments are as follows:		
 Not related (unrelated): This relationship suggests that there is no association between the investigational product and the reported event. 		

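### The SAP defines a TEAE by onset alone, so whether a pre-dose event that worsens after dosing is counted depends on how the site records it

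*SAP*

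**What the plan says.** TEAE incidence is part of the primary safety endpoint (Protocol Section 3; SAP 2.2). The protocol uses the term and expands the abbreviation but does not define it. The only operational definition is in SAP 4.12.1: "A Treatment Emergent Adverse Event (TEAE) is any adverse event that commences after the start of administration of study drug". The incidence, severity and relationship tables in that section are built on TEAEs and serious TEAEs.

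Protocol 8.3.1 contains two statements about events before dosing. One is that "All AEs and SAEs will be collected from the signing of the ICF until the last follow-up visit". The other covers events arising between consent and dosing: they "begin before the start of study drug and after obtaining informed consent will be recorded on the eCRF, and will be considered as medical history".

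Protocol Appendix 3 (Section 10.3) defines an AE to include any unfavourable sign, "symptom, or disease (new or exacerbated) temporally associated with the use of study drug". For pre-existing conditions it excludes only expected fluctuation without worsening. On recording, it says that "Changes in the severity of an AE should be documented to allow an assessment of the AE duration at each level of intensity" can be evaluated. Onset and duration of each episode are required only for intermittent events whose severity changes. Its follow-up section sends new information back to the eCRF page first completed for the event.

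**The concern.** Appendix 3 treats worsening as an AE, while the SAP flag looks only at the start date. If a continuous event keeps its pre-dose start when its grade rises, the flag excludes it, however severe it becomes after ravulizumab/rHuPH20. Any such error goes in one direction: TEAE incidence and maximum severity come out too low, never too high.

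Events can be open at dosing. Screening lasts up to 70 days and may include meningococcal vaccinations. For the prophylaxis, "The first dose of antibiotic will be administered orally on Day -1 in the evening", and it continues after dosing. In cohorts of 6 and 12, one subject moves a reported percentage visibly.

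**Working it through.** The plan has no figure to reproduce, because the point concerns a definition. The check is to follow one event through the rules. Take a hypothetical headache that starts on Day -1 at Grade 1 and reaches Grade 3 on Day 2 without a break.

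**Route A: one AE record from consent.**
1. Protocol 8.3.1 and the Schedule of Activities footnotes start AE collection at consent, so the headache can be an open AE at dosing.
2. Appendix 3 documents severity changes within an AE and puts updates on the original page. Nothing tells the site to open a new record with a new start date. The episode rule does not apply, because the event is continuous.
3. The record therefore naturally keeps its Day -1 start, and under SAP 4.12.1 it did not commence after dosing. It is not a TEAE. It is absent from the TEAE, severity and relationship tables and appears only in the listing of all AEs.
4. If the event became serious after dosing, it could also miss the serious TEAE table for the same reason.

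**Route B: medical history, then a new AE.**
1. Under the other sentence of Protocol 8.3.1 the headache is medical history.
2. Under Appendix 3 the exacerbation is itself an AE. Entered as a new AE dated Day 2, it starts after dosing and is a TEAE at Grade 3.

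The same clinical course gives two different counts. The documents do not say which route applies or how the onset of an exacerbation is dated.

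**Comparison with neighbouring rules.** SAP 4.10 classes a medication that straddles the first dose as concomitant. SAP 4.16 treats an AE with unknown start as treatment-emergent unless it is known to have ended before dosing. An AE with a known pre-dose start that worsens has no rule.

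**Scale per missed subject.** The inputs are the cohort sizes in SAP 3.3 (6, 12, 12, 12, 6) and the summary groups in SAP 4.12 (each cohort, the rHuPH20 cohorts combined, overall). The assumption is that the missed event is the subject's only TEAE. The fall in incidence is 1/n:

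| Group | n | Fall in TEAE incidence |
|---|---|---|
| Cohort 1 or 5 | 6 | 1/6 = 16.7 points |
| Cohort 2, 3 or 4 | 12 | 1/12 = 8.3 points |
| rHuPH20 cohorts combined | 36 | 1/36 = 2.8 points |
| Overall | 48 | 1/48 = 2.1 points |

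If the subject has another TEAE, overall incidence does not change. The severity table can still be wrong, because it counts each subject at the most severe event. In the example, a subject whose other TEAEs were all Grade 1 would be shown as Grade 1 instead of Grade 3.

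**The case against.** The strongest reply is that a reader might infer that worsening events are lost outright, and the documents do not support that. Route B is a genuine capture route: the medical-history rule can help, because a later exacerbation then meets the AE definition in its own right. Nor can the medical-history rule and the within-AE severity rule be combined to prove loss, since an event is one kind of record or the other. That the onset date stays fixed is an inference from the recording text, not a stated rule. All of this stands, and it limits the point to the single-record route.

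A reader might also infer that the design produces many such events. That is unsupported. Subjects with adequate documented vaccination need no new doses. Study vaccinations come at least 28 or 56 days before dosing, and nothing suggests that reactions persist to Day 1. Eligibility screens out clinically significant abnormalities and recent fever.

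Other safety outputs do not use the flag: laboratory shift tables, ECG and vital-sign changes from baseline, injection-site summaries and the full AE listing. The toxicity rules in Protocol 6.7.1 turn on relatedness and grade. This too stands, but these outputs do not replace a TEAE count for headache, nausea or rash, and a listing is not an incidence. Protocol 9.4.2 does promise AE and SAE incidence without the TEAE restriction, but the tables the SAP specifies are limited to TEAEs and serious TEAEs.

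**Conclusion.** The point holds in this form: the SAP's onset-only definition leaves a post-dose worsening of a pre-dose event countable or not, depending on how the site records it. An event kept as one AE record can be left out. An event filed as medical history whose worsening is entered as a new AE is counted.

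The conclusion rests on two readings: that a continuous AE updated on its original page keeps its start date, and that no recording instruction outside these documents says otherwise. The size is 8.3 or 16.7 points per affected subject within a cohort, if the missed event is that subject's only TEAE. How many subjects would be affected is unknown. Applying a rate such as 5% to 10% of 48 (2.4 to 4.8 subjects) would be an assumption with no source in the documents. All safety analyses are descriptive, so no test is affected, and dose-escalation decisions do not depend on TEAE status. The defect lies in the reporting of a primary safety endpoint and is cheap to remove.

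**What to change.** In SAP 4.12.1, define a TEAE as an AE that starts after the start of study drug administration, or that was present before it and worsens in severity or becomes serious afterwards. State that severity tables use the post-dose grade for such events.

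In the protocol, reconcile Section 8.3.1 with Appendix 3: a post-dose worsening of any pre-dose occurrence, including one filed as medical history, is recorded as an AE dated and graded at the worsening. The SAP change alone is not enough, because the documents require no severity grade for medical history, so a worsening could not be identified from that record.

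The cost is a few sentences across the two documents and a short recording instruction for the site. TEAE counts may rise slightly.
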